3.2 Justification for Investigation and Study Design

Catheter ablation of the cavotricuspid isthmus has been a therapeutic mainstay for the treatment of typical atrial flutter for the past decade. The current understanding of the field of catheter ablation makes for a mature marketplace of irrigated, non-irrigated, and contact force catheters for CTI ablation. The intended use and intended use population of the AcQBlate[®] FORCE is identical to those of current RF ablation catheters from other manufacturers approved for the ablation of atrial flutter.

The expected safety rates for the primary safety and efficacy endpoints were derived from a meta-analysis of recently completed IDE trials and publications related to the safety and efficacy of typical CTI dependent atrial flutter ablation (see Table 1). Event rates were estimated from Summary of Safety and Effectiveness Data (SSED), results disclosed on *clinicaltrials.gov*, peer reviewed publications. and were calculated based on the occurrence of events that constitute the primary safety and efficacy endpoints defined in this protocol.

Table 1. Meta-A	nalysis to I	Determine Sam	ple Size f	for Efficacy
-----------------	--------------	----------------------	------------	--------------

Device Trade Name (PMA Number)	Month/Year	n	Efficacy Estimate**
NaviStar [™] DS 8 mm Deflectable Diagnostic Ablation Catheter Celsius [™] DS 8 mm Deflectable Diagnostic Ablation Catheter Stockert 70 RF Generator (model 87001 with software version 001/033) Catheter Interface Cables (models D-1195 and D-1170) (P010068)	09/2002	182	90.1%
IBI Therapy [™] Dual8 [™] Ablation Catheter IBI-1500T6 (USA) Cardiac Ablation Generator (P040042)	11/2005	150	93.3%
Therapy Cool Path Duo TM Ablation Catheter Safire BLU Duo TM Ablation Catheter 1500T9-CP Vi.6 Cardiac Ablation Generator (P110016)	01/2012	188	96.3%
Therapy [™] Cool Flex [™] Ablation Catheter (P110016/ S008)	12/2013	179	98.9%
Blazer [®] Open-Irrigated Ablation Catheter Maestro 4000 [™] Cardiac Ablation System MetriQ [™] Irrigation Pump MetriQ [™] Irrigation Tubing Set (P150005)	02/2016	109	87.2%
		Mean	93.2%
	We	eighted Mean	93.7%

**Bidirectional CTI Block 30-60 minutes following last RF ablation.

Of the SSEDs listed in Table 1, none provided a comprehensive, tabular summary of SAEs that corresponds with the composite list used for the statistical analysis of the primary safety endpoint of the AcQForce Flutter clinical study. The TOCCATTA trial²¹ was the first multicenter, randomized, controlled trial that used direct contact force in human subjects. The overall event rate for right sided ablations was 2.3%. A comparison of reported events within the SSEDs and the TOCCATTA trial to the pre-defined composite safety definitions suggests an approximate SAE mean event rate of 3.0%, and a weighted mean of 2.9% (Table 2). Note that rates reported in individual studies varied between 2.1% and 5.3%. To account for any differences between the AcQForce Flutter study's primary safety endpoint compared to the previous studies used in the meta-analysis, a derived safety event rate of 3% is expected. Based on this, a performance goal is proposed based on an expected rate of 98.5% and a 5.5% statistical margin. This will define the safety population sample size to support a primary safety endpoint with at least 90% power for the planned sample size.

		Acutus Pre-defined SAE								
Device Trade Name (PMA Number)	N	Death	Cardiac perforation / Pericardial Tamponade	Cerebral Infarct or Systemic Embolism	Myocardial Infarct	Major Access Site Complication	Major Bleeding requiring transfusion	Complete Heart Block	Other Device related SAEs / SADEs	Estimated Safety Event Rate
NaviStar [™] DS 8 mm Deflectable Diagnostic Ablation Catheter Celsius [™] DS 8 mm Deflectable Diagnostic Ablation Catheter Stockert 70 RF Generator (model 87001 with software version 001/033) Catheter Interface Cables (models D- 1195 and D-1170) (P010068)	182	Not Specified	Not Specified	Not Specified	Not Specified	1 (0.5%)	Not Specified	1 (0.5%)	2 (1.1%)	2.2%
IBI Therapyr [™] Dual 8 [™] Ablation Catheter IBI-1500T6 (USA) Cardiac Ablation Generator (P040042)	150	Not Specified	Not Specified	Not Specified	1 (0.6%)	Not Specified	Not Specified	Not Specified	7 (4.7)	5.3%
Therapy Cool Path Duo™ Ablation Catheter Safire BLU Duo™ Ablation Catheter 1500T9-CP Vi.6 Cardiac Ablation Generator (P110016)	188	1 (0.5%)	Not Specified	Not Specified	Not Specified	Not Specified	Not Specified	Not Specified	3 (1.6%)	2.1%
Therapy [™] Cool Flex [™] Ablation Catheter (P110016/ S008)	179	1 (0.6%)	Not Specified	1 (0.6%)	Not Specified	Not Specified	Not Specified	Not Specified	2 (1.1%)	2.2%
Blazer® Open-Irrigated Ablation Catheter Maestro 4000 [™] Cardiac Ablation System MetriQ [™] Irrigation Pump MetriQ [™] Irrigation Tubing Set (P150005)	109	Not Specified	1 (0.9%)	1 (0.9%)	Not Specified	1 (0.9%)	Not Specified	Not Specified	0 (0.0%)	2.8%
TOCCATTA ²⁰ (NCT01223469)	152	Not Specified	2 (1.3%)	Not Specified	Not Specified	3 (2.0%)	Not Specified	Not Specified	Not Specified	3.3%
									Average	3.0%
								We	ighted Average	2.9%

Table 2. Estimated Safety Event Rate Based on Pre-defined Serious Adverse Events

The overall acute efficacy rate from this meta-analysis is 93.7%. Of the five studies evaluated, all studies passed their pre-specified acute efficacy endpoint establishing an acceptable procedural efficacy profile for the catheter under evaluation. A performance goal, using a weighted mean based on sample size, was derived from the meta-analysis. The resultant efficacy performance goal with a 10% statistical margin is 83.7%.

The Primary Safety endpoint of subjects free from a pre-specified composite list of procedure/device related Serious Adverse Events through 7-days post ablation using a literature based control comparative analysis will drive the sample size. A maximum of 110 mITT subjects* will be enrolled based on a one sided α 0.05, 90% power, and a 5.5% statistical margin. For the purposes of this study a maximum of 110 patients will be enrolled at twenty sites.

Endpoint	Literature Based Control	Statistical Margin	Performance Goal	Acutus Estimate	90% Power α 0.050
Primary Safety	97%	5.5%	93%	98.5%	110*
Primary Efficacy	93.7%	10%	83.7%	93.7%	85

The following assumptions were used in the calculation of sample size:

Inherent limitations in single arm design will be mitigated by limiting bias and confounders in the protocol, including inclusion/exclusion criteria similar to the trials comprising the meta-analysis, as well as rigorous patient screening and arrhythmia recurrence monitoring.

REPORT OF PRIOR INVESTIGATIONS 4

4.1 **Overview**

In May of 2019, Acutus Medical, via a joint agreement, acquired the Biotronik AlCath Force Sensing Catheter and Qubic Force Sensing Module technology. The AlCath Force catheter was rebranded as the AcQBlate Force Sensing Ablation Catheter and manufacturing was moved to Carlsbad, California. The Qubic Force Sensing Module retained its initial branding.

Following CE Mark approval, Biotronik conducted the post-market, prospective, BIO|CONCEPT AlCath Force study enrolling 30 subjects with PAF and/or typical AFL at 6 sites in Australia. Ablation procedure included PVI only (n=12), CTI only (n=16), and PVI plus CTI (n=2). The study objective was to provide continued clinical evidence supporting the safety and efficacy of the devices and identify additional risks associated with use. Safety endpoints included the collection of all SAEs and serious adverse device effects (SADEs) Acutus Medical, Inc.

through procedure discharge. The efficacy endpoint was the determination of electrical isolation defined as PV isolation for the pulmonary vein (PV) ablation and bidirectional block for the CTI ablations.

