Study Sample Size	The sample size consists of 110 Modified Intent-to-Treat (mITT) subjects, based on using a one-sided α of 0.05, with 90% power. A maximum of 120 Modified Intent-to-Treat (mITT) subjects will be enrolled. mITT subjects are any enrolled subjects who initiate the ablation procedure using the AcQBlate Force Sensing System.
Study Geographies	The AcQForce Flutter Study will be conducted at up to 20 clinical study sites in the USA and Europe.
Study Duration	The clinical study is anticipated to take approximately 12-months to enroll and will include a 30-day follow-up period. Total clinical study duration is anticipated to be approximately 12-18 months. The per patient clinical study duration is expected to be approximately six (6) weeks.

Inclusion	A potential study subject will meet all the following inclusion criteria:
Criteria	1. Subjects are clinically indicated for de novo catheter ablation of typical atrial flutter.
	 At least one (1) documented episode of typical atrial flutter within 180 days (6 months) prior to enrollment, documented by 12-lead ECG.
	3. Age 18 years or older at time of consent.
	4. Subjects are willing and able to provide written informed consent to participate in the study and agree to comply with all follow-up visits and evaluations.
Exclusion Criteria	A potential study subject who meets any of the following exclusion criteria will be excluded:
	1. In the opinion of the Investigator, any contraindication to the planned atrial ablation, including contraindications to anticoagulation therapy and any other significant uncontrolled or unstable medical condition (e.g. sepsis, acute metabolic illness, chronic kidney disease).
	2. Inability to document cavotricuspid isthmus conduction.
	3. Any prior right atrial cavotricuspid isthmus ablation.
	 Any cardiac ablation for non-atrial flutter arrhythmias within 90 days prior to enrollment.
	5. Any patient scheduled or anticipating an AF ablation within the follow-up period.
	 Administration of oral amiodarone within 120 days prior to procedure excluding a one-time IV/oral administration of ≤ 2000 mg in a 24-hour period.
	7. Cardiac surgery within 60 days prior to enrollment.
	8. ST-elevation myocardial infarction (STEMI) within 60 days prior to enrollment
	9. Current unstable angina.
	10. Documented atrial or ventricular tumors, clots, thrombus, within 30-days prior to enrollment.
	11. Any history of a known hematologic disorder (bleeding/clotting).

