6.4.1 Clinical Study Sample Size

The sample size consists of 110 mITT subjects, based on using a one-sided α of 0.05 and at least 90% power for the comparison of each primary endpoint against the corresponding performance goal. A maximum of 120 mITT subjects will be enrolled.

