6.4.2 Clinical Study Site Enrollment

Enrollment at any single clinical center will be limited to 20% of the maximum enrollment. Clinical centers will be informed in writing by the Sponsor when they have met any of the enrollment limits.

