8.8 Study Sample Size Rationale

The sample size requirement for this protocol was determined using the Statistical Analysis System (SAS) Software (Cary, NC) Proc Power one sample proportion using a normal-approximate z test, with at least 90% power and a one-sided 5% significance level.

For the primary safety endpoint, assuming an estimated primary safety rate of 97% and a null hypothesis proportion of 93%, a minimum sample size of 110 subjects is required.

For the primary efficacy endpoint, assuming an estimated primary efficacy rate of 93.7% and a null hypothesis proportion of 83.7%, a minimum sample size of 85 subjects is required.

Therefore, the minimum required sample size for this study will be 110 subjects. A maximum of 120 mITT subjects will be enrolled.

8.9 Statistical Methods for Baseline, Screening, Procedural Experience and Hospital Discharge Data

Demographics, baseline data, including but not limited to relevant descriptors from the medical history, co-morbidities and medications, will be summarized.

Procedural data collection will also be analyzed and summarized.

Continuous variables are summarized as means, standard deviations, medians, and ranges. Categorical variables are summarized as frequencies and percentages. By-Subject listings of baseline and procedural data will be provided.

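### Section 3.2 caps enrolment at 110 while the synopsis, 6.4.1 and 8.8 cap it at 120, no rule closes enrolment in between, and exact safety power falls below the promised 90% from n = 117

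*Combined protocol and SAP*

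**What the plan says.** Protocol 3.2 gives 110 as a ceiling twice: "A maximum of 110 mITT subjects* will be enrolled" and "For the purposes of this study a maximum of 110 patients will be enrolled at twenty sites".

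Three other places give 120. The synopsis has "A maximum of 120 Modified Intent-to-Treat (mITT) subjects will be enrolled", and 6.4.1 has "A maximum of 120 mITT subjects will be enrolled". Section 8.8 uses 110 as a floor: "Therefore, the minimum required sample size for this study will be 110 subjects. A maximum of 120 mITT subjects will be enrolled".

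Section 6.4.2 sets the per-site limit as a share of the same undefined figure: "Enrollment at any single clinical center will be limited to 20% of the maximum enrollment".

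The sizing in 8.8 uses a normal-approximation z test "with at least 90% power and a one-sided 5% significance level", and 6.4.1 makes the power promise for each primary endpoint. The decision rules in 8.2.1 and 8.3.1 are exact: the one-sided 95% Clopper-Pearson lower bound must exceed 93.0% for safety and 83.7% for efficacy. The body of the SAP has no sample size section, and its section 5.9 plans no interim analyses.

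**The concern.** One number cannot be both the most and the fewest subjects the study will treat. Sections 1, 6.4.1 and 8.8 agree with one another, so 3.2 is the outlier. Aligning 3.2 would still leave a band of eleven possible sample sizes and no statement of what ends enrolment within it.

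Three things depend on the answer. The first is power: the z approximation suggests that more subjects can only help, but the exact rule allows failures in whole numbers, so extra subjects can lower power. The second is the site cap, which has two values. The third, and smaller, is error control. In a single-arm study acute block is known during the procedure, so an open stopping point leaves room for a choice made with efficacy results in view.

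**Working it through.** **Inputs.** Safety: null 93.0%, expected 98.5% (protocol 3.2 and the table in 8.1). Efficacy: null 83.7%, expected 93.7% (8.1, 8.8). One-sided alpha 0.05, power 0.90. Candidate n: 110 to 120.

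**Reproducing the plan's figures.** N = [(z₀.₉₅√(p₀(1−p₀)) + z₀.₉₀√(p₁(1−p₁)))/(p₁−p₀)]².
- Safety: [(1.6449 × 0.25515 + 1.2816 × 0.12155)/0.055]² = 109.5, so 110. Reproduced.
- Efficacy, 83.7% against 93.7%: 84.4, so 85. Reproduced.

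By this approximation, safety power rises from 90.2% at 110 to 93.4% at 120.

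**Failures allowed under the exact rule.** With f failures in n, the lower bound L is the 5th percentile of Beta(n−f, f+1).
- Safety, n = 110: f = 3 gives L = 93.10% (pass); f = 4 gives 91.87% (fail).
- Safety, n = 120: f = 3 gives 93.67% (pass); f = 4 gives 92.53% (fail).
- The safety limit is three failures at every n from 110 to 120.
- Efficacy: 11 failures for n = 110 to 115, and 12 for n = 116 to 120. Twelve failures give L = 83.64% at n = 115 (fail) and 83.78% at n = 116 (pass).

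**Exact safety power.** Power = P(X ≤ 3), X ~ Binomial(n, 0.015).
- n = 110: 0.18966 + 0.31771 + 0.26368 + 0.14456 = 0.9156.
- n = 120: 0.16306 + 0.29798 + 0.27000 + 0.16172 = 0.8928.

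| n | Safety failures allowed | Safety power at 98.5% | Safety alpha | Efficacy failures allowed | Efficacy power at 93.7% | Efficacy alpha |
|---|---|---|---|---|---|---|
| 110 | 3 | 91.6% | 4.62% | 11 | 95.5% | 4.24% |
| 115 | 3 | 90.5% | 3.61% | 11 | 94.1% | 2.79% |
| 116 | 3 | 90.2% | 3.44% | 12 | 96.9% | 4.78% |
| 117 | 3 | 89.99% | 3.27% | 12 | 96.7% | 4.42% |
| 120 | 3 | 89.3% | 2.81% | 12 | 96.0% | 3.47% |

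Safety power is below 90% from n = 117. Efficacy power is above 94% throughout.

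**Site cap.** 0.20 × 110 = 22; 0.20 × 120 = 24.

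**Secondary check: a stop chosen with outcomes in view.** An exact recursion gives the chance of meeting the bound at some n from 110 to 120 when the true rate equals the null.
- Efficacy alone: 5.38%. With looks only at 110 and 120: 4.80%.
- Safety alone: 4.62%, the same as at a fixed 110, because the allowed failures never rise.
- Both endpoints at the same n, with true efficacy 83.7% and the endpoints assumed independent: 3.1% if true safety is 97%, 4.9% at 98.5%, 5.2% at 99% and 5.4% at 100%.

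The efficacy excess comes from the step at n = 116. Twelve failures in 110 fail the test, but six further successes make it 12 in 116, which passes.

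**The case against.** The strongest reply is that 8.8 is the governing section and is clear: at least 110, at most 120. The synopsis and 6.4.1 agree, so 3.2 is a background section that was not updated. The 110 in 3.2 also carries an asterisk whose note is not visible in the text and may qualify it. Much of this stands: the intended range is probably 110 to 120. But the second sentence in 3.2 has no asterisk, and 8.8 does not say what closes enrolment inside the range.

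A reader might infer that the open range inflates the trial's type I error. The documents do not support that as a description of the plan. No interim analyses are planned, and any n fixed beforehand keeps efficacy alpha between 2.79% and 4.78%. Going over 5% requires outcomes to be tracked and enrolment extended in order to pass. Section 8.4 also requires both nulls to be rejected, which brings the worst case to about 4.9% at the planned 98.5% safety rate.

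Nor are all outcomes known at once. Safety runs through 7 days and is independently adjudicated, so only acute block is immediate. Sponsor staff attend each procedure (9.7), but 11.17.1 bars them from independently collecting critical endpoint data.

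Finally, the power change is small, 2.3 points from end to end. That is true, but it crosses the plan's own threshold, and in the direction opposite to the one the planning method shows.

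**Conclusion.** The contradiction is real and lies in current body text. Its effects are modest: exact safety power of 91.6% at 110 and 89.3% at 120, short of the promise in 6.4.1 from n = 117, and a site limit of 22 or 24. The site limit depends on which maximum applies, not on where enrolment stops. The type I error point is a conditional risk worth closing with a sentence, not evidence that the test is invalid.

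The power figures rest on a true safety rate of 98.5%. The prose of 8.8 states 97% instead, at which exact power would be 57.9% at 110 and 51.3% at 120. That is a separate and larger discrepancy, and this point does not rely on it. The figures also take n as the number in the safety analysis. That set adds ITT Failure subjects who had the catheter inserted, so it can exceed the mITT count. The joint 4.9% assumes independent endpoints and would pass 5% if true safety were about 99% or better.

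**What to change.** At the next amendment:

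1. Give one target and one maximum mITT number, worded identically in the synopsis, 3.2, 6.4.1 and 8.8.
2. State that enrolment closes when the target count is reached, that only subjects who have already consented may be treated beyond it up to the maximum, and that closure does not depend on endpoint results.
3. Name the number to which the 20% site cap in 6.4.2 applies.
4. Restate exact safety power over the permitted range (91.6% at 110, 89.3% at 120). If the 90% floor in 6.4.1 is kept, set the maximum at no more than 116 instead, remembering that ITT Failure subjects in the safety set count towards that n.

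Item 4 is needed alongside item 2, because a closing rule that still allows 120 leaves n = 117 to 120 open. The cost is wording only, with no added subjects and no change to the tests or performance goals.

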4.2 AlCath Force Ablation Procedure

Electrophysiological examinations during the ablation procedure were performed according to clinical study site preference for PVI and CTI ablations. The AlCath Force catheter and Qubic Force were operated as labeled. Target values for contact force, contact force ranges, and force time integrals (FTI) were at the discretion of the Investigator. The following recommendations were adhered to:

- Maximum tip temperature: 42° C (mandatory).
- Energy delivery \leq FTI of 450 gram seconds (gs) in any catheter position.
- Initial power titration of energy ≤ 25 W. After 15 seconds, the energy could be increased until a transmural lesion was achieved.
- When ablating the posterior wall, a reduction in power and FTI was recommended.
- Irrigation flow rates during mapping and ablation followed the Instructions for Use (IFU).

4.3 Results

Baseline demographics are reported in the Table 3 below:

Characteristic	Mean ± SD
Gender	Male 23
	Female 7
Age	64.7 ± 10.7
Weight (kg)	93.7 ± 17
BMI	30.3 ± 4.8
Systolic BP	142.1 ± 15.9
Diastolic BP	76.5 ± 12.9
Co-Morbidities	Frequency (%)
Ischemic heart disease	5 (16.7)

Page 28 of 82

Hypertension	17 (56.7)
Asthma or chronic lung disease (except COPD)	4 (13.3)
Peripheral vascular disease	2 (6.7)
Diabetes Mellitus	8 (26.7)
Renal dysfunction/chronic renal disease	5 (16.7)
COPD (chronic obstructive pulmonary disease)	5 (16.7)

Severe Adverse Device Effects (SADE)

No deaths or SADEs were reported throughout the duration of the clinical study.

Acute Procedural Success

Acute procedural success was defined as isolation of all four pulmonary veins with demonstrated entrance and exit block in subjects receiving an ablation for AF. Fourteen subjects treated for AF demonstrated acute procedural success (14/14, 100%). For subjects receiving a CTI ablation, acute procedural success was defined as bidirectional block across the cavotricuspid isthmus with conformation via differential pacing. Seventeen subjects (17/18 94.4%) achieved the procedure endpoint.

Device Performance

A total of 38 catheters were used in the 30 procedures. Six device deficiencies were observed (6/38, 15.8%). Three of the device deficiencies required the crossover to another AlCath Force catheter. No device deficiencies were noted with the Qubic Force.

A total of 56 usability parameters were assessed: 27 parameters for the AlCath Force catheter and 29 parameters for the Qubic Force. The assessment of usability of the AlCath Force catheter and Qubic Force was positive with 99% of usability aspects rated as "adequate", "good", or "very good". Approximately 1% of rates were ranked as "poor" or "very poor".

Ablation parameters for the PVI and CTI ablations are outlined in the Table 4 below:

Variable	Subgroup	Data
	(n)*	Mean ± SD
		(min, max)
High Rate Irrigation Flow	CTI Ablation	17.5 ± 3.6
Setting (ml)	(16)	(12, 30)
	PVI Ablation	19.2 ± 5.1
	(12)	(17, 30)

Table 4: BIOCONCEPT AlCath Force Procedure Parameters during RF Ablation

Variable	Subgroup	Data
	(n)*	Mean ± SD
		(min, max)
	CTI plus PVI	17.0 ± 0
	(2)	(17, 17)
-	All	18.1 ± 4.1
	(30)	(12, 30)
Low Rate Irrigation Flow	CTI Ablation	2.0 ± 0
Setting (ml)		(2, 2)
-	PVI Ablation	2.2 ± 0.6
		(2, 4)
-	CTI plus PVI	2.0 ± 0
		(2, 2)
-	All	2.1 ± 0.4
		(2, 4)
Cumulative Irrigation	CTI Ablation	519 ± 267
Volume (ml)		(174, 1100)
-	PVI Ablation	892 ± 441
		(340, 1950)
-	CTI plus PVI	765 ± 101
		(694, 837)
-	All	684 ± 380
		(174, 1950)
Pre-set RF Power (W)	CTI Ablation	30 ± 0
		(30, 30)
-	PVI Ablation	22.9 ± 4.5
		(20, 30)
-	CTI plus PVI	30 ± 0
		(30, 30)
	All	27.2 ± 4.5
		(20, 30)
Maximum RF Power (W)	CTI Ablation	31.3 ± 3.4
		(30, 40)
	PVI Ablation	27.5 ± 2.6
		(25, 30)
Ī	CTI plus PVI	30 ± 0
		(30, 30)
Ī	All	29.7 ± 3.5
		(25, 40)

Variable	Subgroup (n)*	Data Mean ± SD (min, max)
Maximum Tip Temperature	CTI Ablation	36.4 ± 3
Reached (C°)		(31, 42)
	PVI Ablation	34.9 ± 2
		(33, 39)
	CTI plus PVI	38.5 ± 4.9
		(35, 42)
	All	35.9 ± 2.8
		(31, 42)
Cumulative Duration of	CTI Ablation	22.1 ± 12.5
Energy Delivery (min)		(4, 51)
	PVI Ablation	46.1 ± 21.4
		(19, 97)
	CTI plus PVI	39.5 ± 4.9
		(36, 43)
Aimed Contact Force (g)	CTI Ablation	25.6 ± 7.3
		(7.3, 20)
	PVI Ablation	25.0 ± 8.0
		(8.0, 20)
	CTI plus PVI	30.0 ± 0
		(30, 30)
	All	25.0 ± 7.3
		(20, 40)

*N values remain the same for all subgroups

Protocol Deviations

Protocol related deviations were observed in four subjects, including an application of RF power > 40 W (n=2), a minor infraction to the informed consent process, and the enrollment of a subject not eligible based on inclusion/exclusion criteria.

